The Safety and Efficacy of the Transnasal Humidified Rapid-Insufflation Ventilatory Exchange (THRIVE) for Laser Laryngeal Surgery

Study Protocol

NCT03086265

August 12, 2016

STUDY PROTOCOL: THRIVE AND LASER LARYNGEAL SURGERY

1

STUDY OBJECTIVES

1. DETERMINING THE SAFETY OF THRIVE FOR LASER LARYNGEAL SURGERY. Current practice involves the use of specialized ETTs or jet ventilation catheter (JVC) that are laser resistant, but not laser proof. One of the major concerns with their use is the possibility of airway fire. The “fire triangle” requires the presence of an oxidizer (O_2), the ignition source (laser) and the “fuel” (ETT or JVC). If high oxygen concentration (FiO_2) is administered to the patient, the airway fire may happen, with devastating consequences. Thus, a decrease in oxygen concentration (FiO_2) below 30% constitutes current standard of care when ETT or JVC are used. Such low FiO_2 may not be well tolerated by all the patients.

In contrast, during THRIVE the fuel source (ETT or JVC) is removed, the “fire triangle” is disrupted, and safe administration of a higher FiO_2 is possible. Importantly, a completely “tubeless”, non-instrumented surgical field will be greatly enlarged, providing superior operating conditions and access to all parts of the glottis. This should improve operating conditions, decrease surgical time, and potentially lead to better patient outcomes. The safety of THRIVE for laser laryngeal surgery has not been formally investigated, and will be explored in this study.

2. DETERMINING THE SAFE DURATION OF THRIVE FOR VOCAL CORD LASER SURGERY. With the patient anesthetized, apneic, and adequately oxygenated with THRIVE, the build up of carbon dioxide in patient’s blood ($PaCO_2$) and ensuing acute hypercapnic acidosis will be the main factors limiting the duration of THRIVE administration. At present, the rate of $PaCO_2$ rise with THRIVE is suggested to be between 1.1 – 1.8 mm Hg per minute. By using the serial ABG measurements, we will be able to determine the rate of $PaCO_2$ rise during THRIVE and provide clinical guidance for safe administration of THRIVE in the future. We will allow $PaCO_2$ to rise to 75 mm Hg, which is considered a safe level for moderate hypercapnia in patients without significant comorbidities (see Exclusion Criteria).

3. DETERMINING THE OPTIMAL VENTILATORY STRATEGY FOR MAINTAINING SAFE $PaCO_2$ LEVEL DURING THRIVE ADMINISTRATION

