4. DETERMINING THE HEMODYNAMIC CHANGES THAT OCCUR DURING THRIVE IN PATIENTS ANESTHETIZED WITH TOTAL INTRAVENOUS ANESTHESIA USING PROPOFOL AND REMIFENTANIL. The administration of THRIVE requires the conduct of total intravenous anesthesia (TIVA), as delivery of anesthetic gases to the patient is not possible. TIVA with propofol and remifentanil is commonly used for VC laser surgery, and will be employed in this study. Acute hypercapnia and hypercapnic acidosis have been shown to produce an increase in cardiac output, cardiac index, a decrease in systemic vascular resistance, without associated tachycardia and myocardial depression with PaCO₂ ≤ 70 mm Hg in patients who do not have significant comorbidities. These hemodynamic responses will be modified by TIVA with propofol and remifentanil, and we will investigate the extent of these changes to determine cardiovascular safety of THRIVE used in conjunction with TIVA. We will be continuously monitoring the heart rate, arterial blood pressure, cardiac output, cardiac index, and systemic vascular resistance during the surgery using Edwards EV1000 Clinical Platform with FloTrack sensor. Determining hemodynamic changes that accompany THRIVE that is conducted under TIVA with propofol and remifentanil will promote safe use of this technique in clinical anesthesia practice. Using Edwards EV1000 Clinical Platform we also will assess acute hemodynamic changes that may be associated with supraglottic LFJV and HFJV under the conditions of deliberate moderate hypercapnia. Demonstrating the safety and efficacy of THRIVE may make this technique a simple, safe and effective alternative to conventional use of ETT or JV during laser laryngeal surgery in selected patients.

EXCLUSION CRITERIA

1. Patients with significantly decreased myocardial function (ejection fraction < 50%)
2. Patients with abnormal cardiac rhythm and conduction abnormalities, except for patients with isolated, asymptomatic premature atrial and ventricular contractions.
3. Patients with significant peripheral vascular disease, such as those with the symptoms of intermittent claudication.
4. Patients with known significant cerebrovascular disease, such as history of cerebrovascular accidents (CVAs) and transient ischemic attacks (TIAs).
5. Patients with significant renal insufficiency, as manifested by estimated glomerular filtration rate (eGFR) < 60 ml/min/1.73 m².

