The Safety and Efficacy of the Transnasal Humidified Rapid-Insufflation Ventilatory Exchange (THRIVE) for Laser Laryngeal Surgery

Statistical Analysis Plan

NCT03086265

February 24, 2020

The planned sample size for the study was 40 patients (subsequently reduced to 20 due to logistical constraints), randomized 1:1 to receive one of 2 oxygen delivery systems, Transnasal Humidified Rapid- Insufflation Ventilatory Exchange (THRIVE), or endotracheal tube (standard of care).

Anesthesia, surgical, and patient recovery outcomes were summarized using descriptive statistics, with p-values calculated using a 2-sided t-test and Fisher Exact test.

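### The SAP's only between-arm inference is a difference p-value without a confidence interval; at about 10 patients per arm a non-significant result cannot support calling THRIVE a safe alternative to the tube

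*SAP*

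**What the plan says.** The SAP's analysis text is one sentence. It covers three groups of outcomes: "Anesthesia, surgical, and patient recovery outcomes were summarized using descriptive statistics", with "p-values calculated using a 2-sided t-test and Fisher Exact test". It gives no confidence interval, significance level, margin or primary end-point. On size it says "The planned sample size for the study was 40 patients", "subsequently reduced to 20 due to logistical constraints", and that patients were "randomized 1:1 to receive one of 2 oxygen delivery systems".

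The protocol (Study Objectives, 1) makes safety the first objective: "The safety of THRIVE for laser laryngeal surgery has not been formally investigated, and will be explored in this study". The same objective predicts better operating conditions and shorter surgery, and holds out better patient outcomes as a possibility. Study Objectives, 4 closes with the wider hope: "Demonstrating the safety and efficacy of THRIVE may make this technique a simple, safe and effective alternative to conventional use of ETT or JV".

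The end-points measured in both groups (Protocol at a Glance and Study End-Points, 23.b) include surgical time, time to suspension and laryngoscope repositions. They also include lowest SpO2, the PACU recovery profile and the functional recovery profile.

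**The concern.** The end-points measured in both groups serve two kinds of claim. Where the protocol predicts a gain, as for surgical time, a two-sided test of no difference asks the right question. For lowest SpO2 and recovery, THRIVE need not be better to count as an alternative; it must not be importantly worse. A p-value against no difference cannot show that, because a large p-value may mean similar arms or too few patients. Only an interval for the difference separates the two, and the SAP plans none.

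If THRIVE truly lowers oxygen saturation or slows recovery by a moderate amount, the planned output will usually be a non-significant p-value, which could be taken as reassurance. Conversely, if the data do rule out a large deficit, the planned output has no way to say so.

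**Working it through.** **Inputs.** Total 20, allocation 1:1, t-test and Fisher exact test: all from the SAP. Ten per arm is 20 / 2; the SAP does not state it. The two-sided 5% level is an assumption. The documents give no SD, event rate or effect size, so mean differences are in SD units and event counts are illustrations. The sample size itself cannot be reproduced, because no basis is given for 40 and only a logistical reason for 20.

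**1. Precision of a mean difference.** Half-width = t(0.975, 18) × √(2/10) = 2.101 × 0.447 = 0.94 SD. An observed difference of exactly zero would still leave a deficit of up to 0.94 SD inside the interval. At 20 per arm, the size before the cut, it would be 2.024 × √(2/20) = 0.64 SD.

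**2. Chance that a true deficit is non-significant.** This uses the noncentral t with 2n − 2 degrees of freedom and noncentrality d × √(n/2).

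| True deficit d | Noncentrality, n = 10 | Power, n = 10 | Non-significant, n = 10 | Non-significant, n = 20 |
|---|---|---|---|---|
| 0.5 SD | 1.118 | 18.5% | 81% | 66% |
| 1.0 SD | 2.236 | 56.2% | 44% | 13% |

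**3. Yes/no outcomes.** With no control events and k of 10 in the THRIVE arm, the two-sided Fisher p is 2 × C(10,k) / C(20,k).

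- k = 3: 2 × 120 / 1140 = 0.211
- k = 4: 2 × 210 / 4845 = 0.087
- k = 5: 2 × 252 / 15504 = 0.033

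With no control events, half the THRIVE arm must have the event before the test is significant.

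**4. What an interval would show instead.** For 3/10 against 0/10, the Newcombe score interval for the risk difference runs from −4 to +60 percentage points. For 0/10 against 0/10 its upper limit is 1.96² / (10 + 1.96²) = 28 points. In both cases the interval shows what the p-value hides: a large excess remains possible.

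Interval and test can disagree at this size. For 4/10 against 0/10 the Newcombe interval is +4 to +69 points, which excludes zero although Fisher gives 0.087. The interval method should therefore be named in advance.

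**The case against.** The strongest reply is that the study makes no such claim. Safety is to be explored, the sentence about an alternative is conditional, and neither document states a non-inferiority or equivalence aim. That stands. A reader might infer that the sponsor will take p > 0.05 as proof of safety, but nothing in the documents says so. What remains is that the plan has no between-arm result able to support the hoped-for statement.

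Second, much of the safety and physiology question is not a between-arm matter. Serial blood gases belong to the THRIVE arm, and baseline blood gas and troponin are drawn there only. This also stands: the point reaches only outcomes measured in both arms. The SAP also names no separate safety analysis, and an interval between arms does not fill that gap.

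Third, a reader might infer that the tests can exclude no important harm. The figures contradict this. A 1.0 SD deficit is detected 56% of the time, 5/10 against 0/10 is significant, and the documents do not define an important harm.

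Fourth, it is tempting to require a non-inferiority test on lowest SpO2 with a 5-point margin, taken as the gap between the 95% in the exclusion criteria and the 90% in the maintenance instructions. The documents do not support this:

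- The first figure is a baseline room-air criterion and the second an intraoperative prompt for an individual patient. Their difference is not a tolerable gap between arm means.
- Both arms have an instruction that applies below 90%, so the lowest value is itself affected by rescue, which can shrink a real deficit.
- Power would depend on an SD that the documents do not give. With that margin, no true difference and a one-sided 2.5% level, it falls from 94% at SD 3 points to 75% at 4, 56% at 5 and 42% at 6. The claim that 20 patients can settle non-inferiority is therefore unsupported.

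**Conclusion.** The concern holds as a limit on what the planned analysis can conclude. At about 10 per arm and an assumed two-sided 5% level, non-significance is the likely result for a true 0.5 SD deficit (81%) and a common one for 1.0 SD (44%). It also occurs with four events against none. A non-significant p-value on lowest SpO2 or recovery therefore cannot support calling THRIVE a safe alternative, and the SAP provides no interval that could.

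The verdict does not extend to outcomes where a gain is predicted; the two-sided test suits those. It does not show that the sponsor intends the misreading, or that the trial must be recast as a non-inferiority study. The t-test figures assume roughly normal data. Lowest SpO2 has a ceiling and may be skewed, so they are a guide to scale for that end-point.

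**What to change.** In the SAP:

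1. Keep the two-sided tests for outcomes where the protocol predicts a gain, such as surgical time, time to suspension and repositions.
2. For lowest SpO2 and the recovery outcomes, make the THRIVE minus control difference with its 95% confidence interval the main reported result. Use a mean difference for scores and a risk difference with a named exact or score interval for yes/no outcomes.
3. Base any statement that THRIVE is an alternative on what the interval excludes, never on p > 0.05. Where an important deficit remains inside the interval, call the comparison inconclusive or exploratory.
4. Do not make a non-inferiority test a requirement. The SAP is dated February 2020 and written in the past tense. If the sponsor adds a margin, it needs a clinical justification, and a post hoc label if results are already known.

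The cost is a few lines of SAP text and a few more columns in the results tables, with no new patients or data. The drawback is that the published conclusion may be less favourable to THRIVE.
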